**CONFIDENTIAL**

Date: 15 February 2022  
 Version: 3.0  
 Status: Final  
 Page: 17 of 53

**Novo Nordisk**

Additionally, the severity of GH deficiency expressed as IGF-I SDS level prior to any initiation of GH treatment should be collected at baseline, if available.

Data on the number of patients with a minimum of 1-year of follow-up achieving the age-adjusted IGF-I SDS levels up to the upper limit of the normal reference range (0 and +2) will be reported (i) as part of the progress reports in connection with the PSURs - as soon as first data are available and (ii) as part of the interim reporting (data cut 3 and 6 years after FPFV).

Monitoring of safety in this study will be performed from time of enrolment, defined by signing of the informed consent, until the patient's last visit in the study (defined as end of study or withdrawal of informed consent). Adverse events are expected to be captured and reported by the participating sites during routine clinical evaluations (expected every 6-12 months) and any other intermediate contacts with the patient (e.g. phone call etc).

## 9.1.1 Endpoints

### 9.1.1.1 Primary endpoints

Endpoint title	Time frame	Unit
Number of Adverse drug reaction (ADRs)	From baseline (week 0) to end of study*	Count
Incident Neoplasm	From baseline (week 0) to end of study*	Yes/No
Incident Diabetes Mellitus type 2	From baseline (week 0) to end of study*	Yes/No

\*End of study will differ from patient to patient, but can be between 1 week and a maximum of 10 years

### 9.1.1.2 Secondary endpoints

#### 9.1.1.2.1 Safety

Endpoint title	Time frame	Unit
Number of Adverse Events (AEs)	From baseline (week 0) to end of study*	Count
Number of Serious Adverse Events (SAEs)	From baseline (week 0) to end of study*	Count
Number of Medication Errors (incorrect dose administration rate)	From baseline (week 0) to end of study*	Count

\*End of study will differ from patient to patient, but can be between 1 week and a maximum of 10 years

#### 9.1.1.2.2 Clinical parameters

Endpoint title	Time frame	Unit
Change in IGF-I SDS	From baseline (week 0) to end of study*	-10 to +10
Patient achieving IGF-I SDS target (0-+2)	Approximately**12 months after enrolment in study	Yes/No

Protocol  
 Study ID: NN8640-4515  
 UTN: U1111-1264-8642  
 EU PAS No: Pending

**CONFIDENTIAL**

Date: 15 February 2022  
 Version: 3.0  
 Status: Final  
 Page: 18 of 53

**Novo Nordisk**

Change in Weight	From baseline (week 0) to end of study*	kilogram (kg)
Change in Body Mass Index (BMI)	From baseline (week 0) to end of study*	kg/m 
Change in waist circumference	From baseline (week 0) to end of study*	cm
Change in waist-hip ratio	From baseline (week 0) to end of study*	ratio
Change in lipid profile (cholesterol, HDL, LDL, triglycerides)	From baseline (week 0) to end of study*	mg/dL
Change in HbA1C	From baseline (week 0) to end of study*	%
Change in bone density	From baseline (week 0) to end of study*	g/cm 
Change in bone mineral content	From baseline (week 0) to end of study*	g
Change in total body fat-mass	From baseline (week 0) to end of study*	kg
Change in truncal fat-mass	From baseline (week 0) to end of study*	kg
Change in lean body mass	From baseline (week 0) to end of study*	kg
Change in body fat percentage	From baseline (week 0) to end of study*	%
Change in visceral adipose tissue (VAT)	From baseline (week 0) to end of study*	cm 
Change in Liver function (AST, ALT, GGT, bilirubin)	From baseline (week 0) to end of study*	U/L
Change in PRO score, TRIM-AGHD	From baseline (week 0) to end of study*	-100 to +100
Patient reaching satisfactory clinical response	Approximately** 12 months after enrolment in study	Yes/No

\*End of study will differ from patient to patient, but can be between 1 week and a maximum of 10 years

\*\* i.e., the closest routine clinical after 12 months post enrolment

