**Figure 1 Study Design**

**Note:** symbol (  ) Represents interim reporting

The study is planned to collect a broad variety of safety and other clinical parameters data generated during routine clinical care visits and other relevant clinical contacts (e.g. phone calls between patient and clinical site) in AGHD patients treated with commercially available Sogroya® (somapacitan). The duration of the study is planned with patient participation for 5 years or longer up to a total study duration of 10 years, if possible. The main purpose of the study is to observe patients for long-term safety. It is however well known that adult patients on GH therapy, often interrupt or discontinue treatment. Due to this expected dropout from treatment, and in the context of the duration of the study, patients switching from or discontinuing treatment with Sogroya® (somapacitan) will be offered continuation in the study in order to collect post treatment data.

The current study will compare data from a non-interventional registry study (NordiNet® IOS) which was monitoring the long-term use of once daily Norditropin® as a historical comparison group consisting of approximately 2300 AGHD patients enrolled in Europe between 2006 and 2016.

The sample size estimation for this study is based on the incidences for neoplasms reported in Nordinet® IOS. It is estimated that a sample size of 400 patients will be required to rule out the doubling of incidence for neoplasms in patients treated with Sogroya® (somapacitan).

Data on concomitant medication, medical history (adult/ childhood onset of GHD), laboratory parameters including but not limited to hepatic, renal, heart and diabetes status as well as data on neoplasms and medication errors will be collected as part of this study if available per routine clinical practice in order to evaluate safety. Other data which are already available in the medical records or being obtained as part of routine clinical practice, such as IGF- I /IGFBP-3 values, measures of body composition and bone health and PROs, will be collected to support the evaluation of clinical parameters.

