### 9.2.4 Rationale for selection criteria

The study population is comprised of adult patients diagnosed with GHD and treated with commercially available Sogroya® (somapacitan). The study population will include patients naïve and non-naïve to any GH replacement therapy (including Sogroya® (somapacitan)) at time of study enrolment and will also include patients with severe hepatic impairment, patients with New York

Protocol  
 Study ID: NN8640-4515  
 UTN: U1111-1264-8642  
 EU PAS No: Pending

CONFIDENTIAL

Date: 15 February 2022  
 Version: 3.0  
 Status: Final  
 Page: 20 of 53

Novo Nordisk

Heart Association class 2 heart failure and woman on oral oestrogen treatment who are diagnosed with AGHD.

The few inclusion and exclusion criteria of this study will greatly reduce selection bias. As a multicentre, multinational population has been selected the generalizability of the study is evaluated as high. The study is global and can include all ethnic groups.

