### **9.2.7.2 Local Laboratory**

Blood samples obtained from local laboratory in accordance with normal clinical practice should be recorded in the eCRF if available and may include:

Applicable local laboratory reference ranges must be collected and shared with Novo Nordisk.

- **Biochemistry**

- Creatinine
- High-Sensitive C-Reactive Protein
- Alkaline phosphatase

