#### **Continuous secondary endpoints:**

For the following secondary endpoints, the change will be estimated by length of follow-up and by treatment duration. Patients on oral oestrogen therapy and patients with childhood-onset GHD will be addressed in stratified analyses. The effect of a previous GH replacement therapy on the health-related quality of life will be checked in stratified analyses.

- Change in IGF-I SDS
- Change in weight
- Change in BMI
- Change in waist circumference
- Change in waist-hip ratio
- Change in lipid profile
- Change in HbA1C
- Change in bone density
- Change in bone mineral content
- Change in total body fat mass
- Change in truncal fat mass
- Change in lean body mass
- Change in body fat percentage
- Change in VAT
- Change in liver function
- Change in PRO score (TRIM-AGHD)

Protocol  
 Study ID: NN8640-4515  
 UTN: U1111-1264-8642  
 EU PAS No: Pending

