**Novo Nordisk**

### **Categorical secondary endpoints:**

The binary categorisation of the endpoints Patient achieving IGF-I SDS target (0 -+2) and Patient reaching satisfactory clinical response will be used to calculate the proportion (%) of patients achieving these criteria.

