#### Adverse Event (AE)

Any untoward medical occurrence in a patient or clinical investigation subject administered/using a product and which does not necessarily have a causal relationship with this treatment. An AE can therefore be any unfavourable and unintended sign (including an abnormal laboratory finding), symptom or disease temporally associated with the use of a product, whether or not it is considered to be related to the product. An AE may be associated with the use of a drug, a medical device or both.

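### The only laboratory-based liver endpoint is a continuous change in U/L, a unit bilirubin does not have; patient counts above multiples of the local upper limit of normal would be more informative

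*Protocol*

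**What the plan says.** The endpoint table in protocol section 9.1.1.2.2 (Clinical parameters) has one row for the liver, "Change in Liver function (AST, ALT, GGT, bilirubin", running from baseline to end of study. The unit column for that row reads U/L and nothing else. The lipid row of the same table is in mg/dL.

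Section 9.7.2.2 lists "Change in liver function" among the continuous secondary endpoints, next to weight and BMI, and says for all of them that "the change will be estimated by length of follow-up and by treatment duration". The categorical endpoints in the same section are confined to "The binary categorisation of the endpoints Patient achieving IGF-I SDS target (0 -+2) and Patient reaching satisfactory clinical response". No liver category is named.

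Four other places bear on this:
- Section 9.1 lists "laboratory parameters including but not limited to hepatic, renal, heart and diabetes status" among the data collected in order to evaluate safety.
- Section 9.2.7.2 requires that "Applicable local laboratory reference ranges must be collected and shared with Novo Nordisk".
- Section 9.2.4 says the population "will also include patients with severe hepatic impairment".
- Appendix A counts as a possible adverse event "any unfavourable and unintended sign (including an abnormal laboratory finding", and section 9.2.7.1 requires all adverse events to be recorded.

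**The concern.** There are two separate issues. The first is an error on the page: one of the four tests in the endpoint cannot be reported in the unit given for it.

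The second is whether the endpoint fits its purpose. Hepatic results are collected partly for safety, and a liver safety problem usually shows as large rises in a few patients, not as a shift in everybody. A summary of change across the cohort is insensitive to that pattern. The values also come from local laboratories in many countries, and section 9.9 itself names local differences in laboratory analyses as a source of information bias. The same change in U/L can mean different things against different local upper limits. The protocol obtains the reference ranges that would put results on a common scale, but the endpoint it defines is not on that scale.

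At stake is a liver summary that could look neutral in the interim and final reports while a few patients had marked elevations.

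**Working it through.** **Unit.** No calculation is needed. AST, ALT and GGT are enzyme activities, for which U/L is appropriate. Bilirubin is a concentration (for example mg/dL or µmol/L). The table assigns U/L to all four.

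**Plan's own figure.** The protocol gives no numerical value for any liver outcome, so there is nothing to reproduce.

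**Dilution illustration.** All inputs here are assumptions except the planned enrolment of 400 (section 9.2.1). Suppose n patients are tested, k of them rise by r U/L, and the rest change by 0 on average with SD s.

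- Mean change = k·r/n.
- Variance of change ≈ s² + p(1−p)r², with p = k/n.
- 95% half-width = 1.96 × SD/√n.

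Case n = 300, k = 3, r = 300, s = 15:

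- Mean = 3 × 300/300 = 3.0 U/L.
- Variance = 225 + 0.01 × 0.99 × 90,000 = 225 + 891 = 1,116, so SD ≈ 33.4.
- Half-width = 1.96 × 33.4/√300 ≈ 3.8, giving a CI of about −0.8 to 6.8.
- In simulation the interval excludes zero in about 18% of runs. Over 200 to 400 tested, 2 to 4 affected and rises of 200 to 400 U/L, the figure runs from about 4% to just under one half.

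Case n = 400, r = 200, with s from 10 to 20 (here the affected patients are given no background variation):

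| Patients with the rise | Mean change (U/L) | 95% half-width (U/L) |
|---|---|---|
| 2 | 2 × 200/400 = 1.0 | 1.7 to 2.4 |
| 4 | 4 × 200/400 = 2.0 | 2.2 to 2.8 |
| 8 | 8 × 200/400 = 4.0 | 2.9 to 3.4 |

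With 2 or 4 affected patients the shift stays inside its own half-width. With 8 it does not, so the dilution argument applies to a few cases and fades as they become more frequent.

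**Same data as a count.** If the 4 of 400 patients crossed a prespecified multiple of the upper limit of normal, the report would show 4/400 = 1.0% (exact 95% CI 0.27% to 2.54%). The four patients would be visible as such.

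**The case against.** A reader might infer that liver safety is analysed in no other way, so that severe rises would vanish from the reports. The protocol does not support that. An abnormal laboratory finding can be an adverse event (Appendix A). ADRs are summarised by system organ class and preferred term, with patient numbers, proportions and rates (section 9.7.2.1), and AEs and SAEs are analysed in the same way (section 9.7.2.2). A marked rise therefore has a patient-level route into the reports. The limit of that route is that no laboratory threshold triggers a report and that liver events are not among those needing additional data collection (section 11.3). Capture rests on individual judgement.

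Two further readings go beyond the text. Section 9.7.2.2 says only that the change will be estimated. That the summary will be a mean is an inference, though a natural one for a continuous endpoint. Section 9.2.7.2 gives no purpose for the reference ranges, so it cannot be said that they are collected to detect liver injury.

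Three other objections carry weight:
- Threshold and shift tables are commonly left to the SAP, which is not at hand, so their absence from the protocol is not itself a fault. What stands is the endpoint that the protocol does state: a continuous change in one unit.
- A summary that showed the SD or range would give the pattern away. In the first case above the SD of change rises from 15 to about 33, and the maximum lies near 300 U/L.
- Wide starting values do not by themselves widen within-patient change, and patients with severe hepatic impairment may exceed a fixed multiple of normal at baseline. A threshold count alone would misclassify them, which is why it needs a shift from baseline beside it.

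Finally, the special-focus risks are neoplasms, type 2 diabetes and medication errors, not liver injury.

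**Conclusion.** The point holds as a minor one. The bilirubin unit is wrong whatever the SAP says, although that error alone is close to clerical. Beyond it, the protocol's only laboratory-based liver endpoint is a raw change score. That is a weaker choice than a patient-level summary on the scale of the local upper limit of normal, given the mixed laboratories, the stated safety purpose and the reference ranges already required.

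The size of the dilution is illustrative: a mean shift of 1 to 3 U/L, inside its own 95% half-width, when 2 to 4 of 300 to 400 patients rise by 200 to 300 U/L. It depends on an assumed SD of change of 10 to 20 U/L and on the mean being the summary reported. The endpoint is secondary and descriptive, and neither the primary endpoints nor the sample size is touched.

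**What to change.** In section 9.1.1.2.2, keep U/L for AST, ALT and GGT and give bilirubin its own concentration unit.

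In section 9.7.2.2, with the detail in the SAP:
- Express the four tests as multiples of the local upper limit of normal, using the ranges collected under section 9.2.7.2.
- Report the number and proportion of patients whose highest on-treatment value exceeds prespecified multiples.
- Add a shift table from baseline, so that patients enrolled with hepatic impairment are read against their own starting category.
- Keep the change summary as supportive.

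The cost is a corrected table entry, some analysis wording and additional summary tables from data already planned. No new assessments are needed. The downside is that values without a reference range cannot be classified; their number should be reported.

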### 9.1.1.3 Exploratory endpoints

Endpoint title	Time frame	Unit
AGHD Work Study Impact (WSI)	From baseline (week 0) to end of study*	-10 to +10 Annual rate of sick days and physician visits
Number of anti-diabetic medications for patients with diabetes mellitus type 2 at baseline	From baseline (week 0) to end of study*	count of ATC code

\*End of study will differ from patient to patient, but can be between 1 week and a maximum of 10 years

### 9.1.2 Treatment of patients

Patients will be treated with commercially available Sogroya® (somapacitan) according to routine clinical practice at the discretion of the treating physician. The decision to treat a patient with Sogroya® (somapacitan) must be made prior to and independently from the decision to include the patient in this study.

Protocol  
 Study ID: NN8640-4515  
 UTN: U1111-1264-8642  
 EU PAS No: Pending

**CONFIDENTIAL**

Date: 15 February 2022  
 Version: 3.0  
 Status: Final  
 Page: 19 of 53

**Novo Nordisk**

Novo Nordisk will not provide any medicinal products during the conduct of the study.

## 9.2 Setting

### 9.2.1 Study population

Patients for this study will be included globally from centres in countries where patients will be treated with Sogroya® within the planned recruitment timelines of the study.

Planned number of patients to be included globally: 400

Planned number of patients to complete the study: 400

Anticipated number of patients to be included in each country: depending on availability and commercial uptake of Sogroya® in relevant countries.

Planned time period for the study: 15 Dec 2022-15 Dec 2032

### 9.2.2 Inclusion criteria

For an eligible patient, all inclusion criteria must be answered “yes”.

1. Signed consent obtained before any study-related activities (study-related activities are any procedure related to recording of data according to the protocol).
2. The decision to initiate treatment with commercially available Sogroya® (somapacitan) has been made by the patient and the treating physician before and independently from the decision to include the patient in this study.
3. Male or female, age above or equal to 18 years assigned to Sogroya® (somapacitan) treatment at the time of signing informed consent.
4. Diagnosis of adult growth hormone deficiency (AGHD) as per local practice

### 9.2.3 Exclusion criteria

For an eligible patient, all exclusion criteria must be answered “no”.

1. Previous participation in this study. Participation is defined as signed informed consent
2. Mental incapacity, unwillingness or language barriers precluding adequate understanding or cooperation
3. Patients with hypersensitivity to the active substance or to any of the excipients.
4. Patients with active malignancy or in treatment for active pre-existing malignancy.
5. Patients with acute critical illness, suffering from complications following open heart surgery, abdominal surgery, multiple accidental trauma, acute respiratory failure or similar conditions per investigator judgement.

### 9.2.4 Rationale for selection criteria

The study population is comprised of adult patients diagnosed with GHD and treated with commercially available Sogroya® (somapacitan). The study population will include patients naïve and non-naïve to any GH replacement therapy (including Sogroya® (somapacitan)) at time of study enrolment and will also include patients with severe hepatic impairment, patients with New York

Protocol  
 Study ID: NN8640-4515  
 UTN: U1111-1264-8642  
 EU PAS No: Pending

CONFIDENTIAL

Date: 15 February 2022  
 Version: 3.0  
 Status: Final  
 Page: 20 of 53

Novo Nordisk

Heart Association class 2 heart failure and woman on oral oestrogen treatment who are diagnosed with AGHD.

The few inclusion and exclusion criteria of this study will greatly reduce selection bias. As a multicentre, multinational population has been selected the generalizability of the study is evaluated as high. The study is global and can include all ethnic groups.

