### **9.2.8.8 Dosage, titration, and adherence**

The Sogroya® (somapacitan) dosing information at study entry and any changes to the dosing during the study must be recorded in the eCRF. For patient naïve to Sogroya® (somapacitan)

Protocol  
 Study ID: NN8640-4515  
 UTN: U1111-1264-8642  
 EU PAS No: Pending

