### 9.7.2 Statistical methods

#### 9.7.2.1 Analysis of primary endpoints

The primary endpoints are the number of Adverse Drug Reactions (ADRs), incident neoplasms, and incident T2D from baseline (week 0) up to end of study (week 520).

Frequencies of ADRs during the study period will be summarised by MedDRA SOC and PT. This summary is displayed with number and proportion of patients with at least one event, number of event and event rate (events per 100 patient-years of exposure).

The primary objective of the study is to evaluate safety of once weekly dosing of Sogroya® (somapacitan) in AGHD patients over a study period up to 10 years, and analysis of ADRs will be one of the tools for achieving this. Adverse drug reactions will be analysed using descriptive statistics based on the ‘on treatment’ observation period (primary evaluation) and ‘in-study’ observation period (secondary evaluation) within the study period. The ADRs will be summarised by treatment, MedDRA (Medical Dictionary for Regulatory Activities) system organ class and MedDRA preferred term. The descriptive statistics will include the number and percentage of patients who experienced ADRs, the number of events and rate per 100 person years. ADRs will be listed by treatment and patient with information on severity, relationship to study product and demographics. ADRs with onset before first dosing will be reported in a separate listing.

In addition, incidence rates will be calculated for the endpoints Neoplasm and Diabetes Mellitus type 2.

Results will be reported separately for treatment-naïve and prevalent users of GH replacement therapy, and patients with a history of neoplasia and diabetes mellitus 2 will be addressed in stratified analyses.

For historical reference the primary evaluation, i.e. the on-treatment analysis, will be compared to the same results reported from the Nordinet® IOS database. It is not expected that there will be big differences in the baseline characteristics between the Nordinet® adult population and the population investigated in this study. If there are big differences between baseline characteristics, a matching procedure will be considered when making the comparison. In addition, a sensitivity analysis will be performed, restricting the primary evaluation to a European population only.

Protocol  
 Study ID: NN8640-4515  
 UTN: U1111-1264-8642  
 EU PAS No: Pending

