### **9.7.2.2 Analysis of secondary endpoint(s)**

Analyses in the following specific populations of patients will be conducted: Females on oral oestrogen therapy; Adult-onset GHD; Childhood-onset GHD, transition phase from 18 to 25 years and patients switching from daily or other weekly GH treatment after the time of enrolment in the study. Results will be reported separately for treatment-naïve and prevalent users of GH replacement therapy.

Stratified analyses will be performed according to the IGF-I levels (IGF-I SDS [-2, 0], [0, +2] and >+2) at baseline.

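### The primary-endpoint strata do not separate patients already on Sogroya at entry from GH-experienced patients newly starting it, so the pooled comparison with NordiNet is open to prevalent-user selection

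*Protocol*

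**What the plan says.** **Who enters.** Inclusion criterion 3 (section 9.2.2) reads "Male or female, age above or equal to 18 years assigned to Sogroya" treatment when consent is signed. It sets no new-initiator window. Section 9.2.4 confirms the breadth: "The study population will include patients naïve and non-naïve to any GH replacement therapy (including" Sogroya). Section 6 plans recruitment from 15 Dec 2022 to 15 Dec 2027, so a late entrant may have several years of prior use.

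**Who is kept out.** Exclusion criterion 4 (section 9.2.3) covers "Patients with active malignancy or in treatment for active pre-existing malignancy". It is applied at study entry.

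**How the primary endpoints are split.** Section 9.7.2.1 states: "Results will be reported separately for treatment-naïve and prevalent users of GH replacement therapy". It adds that "patients with a history of neoplasia and diabetes mellitus 2 will be addressed in stratified analyses". The on-treatment result is then compared with NordiNet IOS.

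**Related text.** Section 9.7.2.2 lists, for the secondary endpoints, "patients switching from daily or other weekly GH treatment after the time of enrolment in the study". Section 9.2.8.8 asks for titration details with the words "For patient naïve to Sogroya", so Sogroya-naïve status is known at entry. On selection, section 9.2.4 states: "The few inclusion and exclusion criteria of this study will greatly reduce selection bias".

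**The concern.** A patient already on Sogroya at consent has passed through a filter that a new starter has not. Anyone who stopped because of an early adverse reaction is no longer on the drug and does not enrol. A malignancy that arose on Sogroya and is active at consent leads to exclusion. Type 2 diabetes or a benign neoplasm that arose on Sogroya before consent is recorded as baseline illness or medical history (sections 9.2.8.5 and 9.2.8.6), so it is not an incident event. Section 9.1 itself notes that adults on GH often interrupt or stop treatment, so some depletion is to be expected.

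The stated strata put a patient with two years on Sogroya together with a daily-GH patient taking a first Sogroya dose. At stake is whether a reader of the primary tables, and of the NordiNet comparison, can tell how much of the result comes from patients selected for having tolerated the drug. This is separate from the question of when person-time starts: the selected group remains even if time is counted only from consent.

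**Working it through.** **1. Who falls in which primary stratum**

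| Patient at consent | Stratum in 9.7.2.1 | Prior Sogroya? |
|---|---|---|
| No previous GH of any kind | GH-naïve | No |
| On another GH, first Sogroya dose after consent | Prevalent GH user | No |
| Already on Sogroya, any duration | Prevalent GH user | Yes |

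The third row follows because section 9.2.4 counts Sogroya among the GH replacement therapies. The second and third rows share a stratum. The history-of-neoplasia and history-of-diabetes strata do not identify prior Sogroya use. The switcher group in 9.7.2.2 comes close to the second row, but it is listed for the secondary endpoints only.

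**2. Size for ADRs (illustration; all inputs are assumptions)**

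The protocol gives neither the share p of prior Sogroya users nor the time pattern of ADRs. Assume that the ADR rate is k times r in the first Sogroya year and r afterwards, that prior users enter after that first year, and that everyone is followed for 5 years from consent.

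- New-user 5-year mean rate = (k·r + 4r)/5, which is 1.2r for k = 2 and 1.4r for k = 3.
- Prior-user rate = r.
- Pooled rate = (1 − p)·new + p·r.

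| k | p | Pooled 5-year rate | Relative to new users | First-study-year rate relative to new users |
|---|---|---|---|---|
| 2 | 0.2 | 1.16r | −3.3% | −10.0% |
| 2 | 0.4 | 1.12r | −6.7% | −20.0% |
| 3 | 0.2 | 1.32r | −5.7% | −13.3% |
| 3 | 0.4 | 1.24r | −11.4% | −26.7% |

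The last column is [(1 − p)·k + p]/k − 1.

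**3. Size for neoplasm**

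Let f be the share of prior users and s their neoplasm rate relative to new users, with equal person-time. Then pooled/new = 1 − f + f·s. With s = 0.5 this is 0.95 (f = 10%), 0.875 (f = 25%) and 0.75 (f = 50%). These values assume s below 1. If longer exposure raises neoplasm risk, s exceeds 1 and the pooled rate lies above the new-user rate. Nothing in the protocol fixes s.

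**4. What restricting the main comparison to new users would cost**

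The plan's own figure comes first. In section 9.5, an observed incidence of 2% in 400 patients has a 95% interval of 0.9 to 3.9, which excludes 4%. The exact (Clopper-Pearson) interval for 8/400 is 0.87% to 3.90%, so the figure reproduces. At smaller sizes and close to 2%:

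| New users | Prior-user share | Cases | Exact upper 95% limit |
|---|---|---|---|
| 360 | 10% | 7 | 3.97% |
| 320 | 20% | 6 | 4.04% |
| 300 | 25% | 6 | 4.30% |
| 240 | 40% | 5 | 4.79% |
| 200 | 50% | 4 | 5.04% |

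The ability to exclude a doubling survives only if prior users make up about 10% of the cohort or less.

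**The case against.** The best defence has four parts.

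- **The strata already do something.** A reader might infer that the plan never separates prior Sogroya users from new ones. The protocol does not support that: the GH-naïve stratum is reported for the primary endpoints and can hold only new Sogroya users, and post-enrolment switchers are listed for AEs and SAEs among the secondary endpoints. This stands. The gap is confined to the pooled result and the prevalent stratum.
- **Direction.** A reader might infer that neoplasm and diabetes rates are biased downwards. That does not follow. Both endpoints are incident events from baseline, and setting earlier cases aside is normal delayed entry. The later rate falls only if susceptible patients have been depleted, and longer prior exposure could equally raise it. This also stands.
- **It is a detail for the analysis plan.** One more subgroup split could be specified there. This stands only in part, because the protocol itself fixes the primary strata and makes a firm claim about selection bias.
- **Comparability with NordiNet.** The protocol does not say whether the NordiNet patients were new or existing Norditropin users. Section 9.9 states that the comparator shares the same potential limitations. Restricting only the Sogroya side could therefore create an asymmetry. This stands, and it argues against changing the main comparison.

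Section 9.9 does acknowledge selection bias and lists previous GH treatment as a potential confounder. However, the selection it describes comes from willingness or ability to take part and from underdiagnosis. Selection through earlier use of the study drug is not mentioned.

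**Conclusion.** The concern holds in limited form. Patients already on Sogroya are eligible whatever their prior duration, a malignancy active at consent is barred even if it arose on the drug, and the primary strata place these patients with GH-experienced new starters. The pooled on-treatment result compared with NordiNet is therefore open to prevalent-user selection that the primary tables do not isolate.

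The size cannot be derived, because the share of prior users, their prior duration and the time pattern of events are not given. Early ADRs would probably be understated. If first-year rates are 2 to 3 times later rates and 20% to 40% of patients enter after that year, the shortfall is 3.3% to 11.4% over 5 years and 10% to 26.7% in the first study year. For neoplasm and diabetes the direction is uncertain. The unqualified sentence on selection bias in section 9.2.4 claims more than the design supports. This should be corrected, but it does not invalidate the study.

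**What to change.** In section 9.7.2.1:

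- Classify every patient by first-dose date as Sogroya-new (first dose on or after consent) or Sogroya-prior (first dose before consent).
- Report all three primary endpoints for both groups, next to the GH-naïve/prevalent split, and give the distribution of prior Sogroya duration.
- Show the NordiNet comparison in Sogroya-new patients as a sensitivity analysis, and keep all patients as the main comparison so that the precision planned in section 9.5 is retained.

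Qualify the selection-bias sentence in section 9.2.4, and name prevalent-user selection as a limitation in section 9.9.

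The cost is small. Dosing at entry and Sogroya-naïve status are already recorded under section 9.2.8.8, and the observation periods in section 9.7.1 already need the date of first administration. Eligibility and sample size do not change. The downside is some extra tables and less precise subgroup estimates.
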